### III. SUBJECT SELECTION

We will select 24 volunteer subjects (male and female) between the ages of 18-50 years. The subjects will be recruited using:

- An announcement of the study distributed through the Partners Public Affairs distribution list.

All study subjects will be American Society of Anesthesiologists (ASA) physical status classification P1. That is, all study subjects will be fit and healthy. A complete medical history will be taken and a complete physical examination will be given to rule out active and chronic medical problems.

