#### Remuneration

For successful completion of this protocol, subject remuneration will be \$800. If the study subject is unable to complete the entire protocol, pro-rating of this remuneration will be as follows:

- Study subjects who complete the medical screening evaluation but do not begin the anesthesia portion of the study will receive \$50.
- Study subjects who complete the medical screening evaluation, and one anesthesia study visit will receive \$250.
- Study subjects who complete all study portions will receive \$800.

Parking vouchers will be available on study days.

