**Screening Visit:**

All subjects will complete a screening visit. Study subjects will arrive at the study site to undergo screening to ensure that they meet the basic inclusion/exclusion criteria for the study and give written informed consent. All questions will be explained as needed. All women of childbearing age will be tested for pregnancy. A urine hCG pregnancy test will be performed. If the test performed comes back negative for pregnancy, the subject will be enrolled. If the test performed comes back positive for pregnancy or the subject is breastfeeding, the subject will not be enrolled in the study. If the test performed comes back borderline, we perform another test.

Consent Procedures: Prior to the study, each subject will sign an informed consent form. The investigator obtaining consent will explain in detail the protocol of the study, its purpose and potential benefits to the society. Subjects will be informed that if they feel uncomfortable with the study, they can choose to terminate the study at any time.

Physical Examination: The subjects will be given a standard pre-anesthetic physical examination. Particular attention will be paid to the subject's airway anatomy and neurologic function. Any abnormal findings on physical examination will be reason for exclusion from the study. Abnormal findings will be reported to the subjects and recommendations for medical follow-up will be given as needed.

Screening Tests: A complete blood count, blood glucose level, liver function tests (LFTs), blood urea nitrogen (BUN), and creatinine (Cr) level will be obtained at the initial screening visit. For inclusion into the study protocol, each subject will be required to have a platelet count, blood glucose, BUN levels, Cr levels, white blood cell count, hemoglobin, differential and LFTs within 2 times the upper and lower limit of normal. Any subject who tests positive for any "street drugs" (amphetamine, barbiturates, benzodiazepines, cannabinoids, cocaine, opiates, or phencyclidine) may be excluded from the study. An ECG will also be performed.

Randomization: Visits 1 and 2 will be randomized to determine their order of occurrence: sevoflurane only vs. sevoflurane with ketamine.

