**Study Visit 1 and 2:**

Study subjects will arrive at the study site and confirmation of the study subjects' fasting status (minimum 8 hours) will be made. A urine sample will be obtained for a toxic substance screen and for female study subjects, pregnancy testing.

Blood Draws: For all subjects, we will acquire blood samples during Study Visits 1 and 2. The blood draws taken before and after anesthetic exposure will comprise the following: 1.) approximately 2 ml of whole blood for analysis using the 44-analyte TruCultureMAP. Analytes in this map include interleukin 6 and TNF-alpha and, 2.) approximately 13 ml of blood will be acquired processed into serum and stored for downstream studies and

confirmatory assays of TruCultureMAP results.

An EEG montage with a maximum of 256 channels will be placed on the subject. Standard physiological monitors for anesthesia will be placed including: electrocardiogram, pulse oximeter, and non-invasive blood-pressure cuff. End-tidal CO2 measurements will be made by way of a capnogram attached to the expiratory port on the breathing circuit. Galvanic skin response will also be measured. A cuff pain delivery device will be attached to the gastrocnemius area of the lower leg. Baseline vital signs will then be taken. A peripheral intravenous line will be placed and an infusion of ringer's lactate or normal saline will be started. Baseline physiologic measurements will be taken.

The study protocol will be divided into 3 segments. These segments are defined in order as: Baseline Recording; Induction and Recovery from Hypnosis; Post-Anesthesia Recovery.

One time before and one time after the study period, a calibrated cuff pain stimuli will be delivered to the gastrocnemius area of the lower leg using a validated cuff pain device titrated to 8-9/10 pain. A computer controlled air compressor (Hokanson Rapid Cuff Inflator) will inflate the cuff to a pre-specified pressure, and maintain the pressure at that level. Pressure will be maintained for up to 5-minutes to evaluate brain, cardiovascular, and subjective response to experimental pain. One advantage to using cuff algometry pain is that unlike more superficial methods (e.g. heat pain), cuff pain responses are unaffected by sensitization or desensitization of the skin, indicating that this procedure primarily assesses sensitivity in muscle and other deep tissues.

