## **VI. BIostatistical Analysis**

We are using an endpoint of performance score on the Global Precedence task to guide sample size determination. Our null hypothesis is the average within subject difference in performance score for sevoflurane compared to sevoflurane/ketamine is zero. Our

alternative hypothesis is the average within subject difference in performance score for sevoflurane compared to sevoflurane/ketamine is 3. If we assume that the variance in performance score is 9, a type I error of 0.05 and a minimum power of 0.90 for a one-sided z-test, the sample size determinations for our study is 9. Therefore, we should detect a clinically relevant improvement in performance score if we successfully enroll only 9 subjects. To account for data unanticipated events that may lead to poor data quality or data loss, we are proposing to enroll 12 subjects.

EEG acquisition Preprocessing: Continuous EEG will be recorded with up to 256 channels. All data will be stored for subsequent off-line analysis. We will apply an anti-aliasing filter and down-sampled the EEG data to 500 or 250 Hz before analysis. Bandpass filtering of the acquired signal will vary depending upon the features of the EEG data of interest. EEG signals will be remontaged to a nearest-neighbor Laplacian reference, using distances along the scalp surface to weigh neighboring electrode contributions. Trigger signals will be sent from the stimulus delivery system to the EEG recording system to tag the stimulus events for subsequent binning, temporal epoching and averaging of EEG data into the relevant evoked potential averages according to stimulus type and experimental condition.

Video recording to assess level of arousal: Video of the study subject may be recorded during the baseline and induction and recovery from hypnosis periods to assess the study subject's level of arousal. In particular, from clinical experience and previous studies, we note that subjects will exhibit varying levels of arousal after the loss of consciousness, visible in terms of spontaneous movement, which can be recorded on video and then correlated with the EEG. Permission to record video for these data analysis purposes will be obtained from the main research consent form. The video recordings will be stored in a locked file in the investigators office.

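### Section III selects 24 volunteers, Section VI proposes enrolling 12, and nothing in the text reconciles the two

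*Combined protocol and SAP*

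**What the plan says.** Section III (Subject Selection) gives the first figure: "We will select 24 volunteer subjects (male and female) between the ages of 18-50 years". It then sets a condition on the people it describes: "All study subjects will be American Society of Anesthesiologists (ASA) physical status classification P1".

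Section VI (Biostatistical Analysis) gives the second. The sizing endpoint is the Global Precedence score: "Our null hypothesis is the average within subject difference in performance score for sevoflurane compared to sevoflurane/ketamine is zero". The alternative is a mean difference of 3. The remaining inputs are "variance in performance score is 9, a type I error of 0.05 and a minimum power of 0.90 for a one-sided z-test". The result is 9, and to cover poor or lost data "we are proposing to enroll 12 subjects". No loss rate is given.

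Two statements in Section IV fix the design. Under Screening Visit: "Visits 1 and 2 will be randomized to determine their order of occurrence: sevoflurane only vs. sevoflurane with ketamine". Under Study Visit 1 and 2: "For all subjects, we will acquire blood samples during Study Visits 1 and 2".

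**The concern.** Both figures stand in current protocol text and differ by a factor of two. The number of people to be anaesthetised is a core parameter of the protocol. If 12 is meant, Section III reads as twice the intended recruitment. If 24 is meant, the additional 12 people have no justification in the document, and Section VIII says that participants gain nothing directly. A reader comparing final enrolment with the plan could not tell whether 12 is completion or the halfway point, or whether a thirteenth subject is planned or excess.

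**Working it through.** **Inputs (Section VI).** Mean within-subject difference 3; variance 9 (SD 3); one-sided alpha 0.05, z = 1.645; power 0.90, z = 1.282.

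**The plan's own figure.** For a one-sample z-test of the within-subject difference:

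n = (1.645 + 1.282)² × 9 / 3² = 8.56, rounded up to 9.

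This reproduces the 9, taking 9 as the variance of the within-subject difference. It is a total, because each subject supplies one difference. Moving from 9 to 12 implies a loss of 3/12 = 25%. Moving from 9 to 24 would need 15/24 = 62.5%. Neither rate is stated.

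**Can 24 be derived from the stated inputs?**

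| Variant | n |
|---|---|
| Paired z, one-sided, difference variance 9 (as stated) | 9 |
| Paired z, two-sided, difference variance 9 | 11 |
| Paired z, one-sided, difference variance 18 (per-visit variance 9, zero correlation) | 18 |
| Paired z, two-sided, difference variance 18 | 22 |
| Two independent groups, one-sided | 18 per group, 36 in total |
| Two independent groups, two-sided | 22 per group, 44 in total |

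None gives 24. The 18 in the third row, inflated for 25% loss, gives 18/0.75 = 24, but that needs a different variance and contradicts the stated 9 and 12.

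**Possible readings of 24.**

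- *Two parallel arms of 12.* Excluded: each subject has both visits, and the hypothesis is within-subject.
- *24 screened, 12 enrolled.* Possible. The Remuneration text applies the term study subjects to people who are only screened: "Study subjects who complete the medical screening evaluation but do not begin the anesthesia portion of the study". Against it, Section III requires all study subjects to be ASA P1, a status that screening is there to establish, and no screening target or screen-failure rate is given.
- *12 subjects × 2 visits = 24 visits.* Section III counts volunteers, not visits.
- *12 per visit order.* The 9 is a total, so the 12 built on it is also a total.

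**What depends on it.** Anaesthesia visits: 12 × 2 = 24, or 24 × 2 = 48. Power on the plan's z-test is Φ(3√(n/9) − 1.645):

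- n = 9: Φ(3.000 − 1.645) = 0.912
- n = 12: Φ(3.464 − 1.645) = 0.966
- n = 24: Φ(4.899 − 1.645) = 0.999

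The gain from 12 to 24 is 0.9994 − 0.9656 = 0.034.

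**Side check on the 9.** The z-test treats the SD as known. If it is estimated, a one-sided paired t-test (df = n − 1, non-centrality 3√(n/9)) has power 0.862 at 9 completers, 0.898 at 10, 0.924 at 11, 0.945 at 12 and 0.999 at 24. Adjusting for period as well (df = n − 2, SE = √[(9/4)(1/n₁ + 1/n₂)], visit orders split 4/5, 6/6 and 12/12) gives 0.849 at 9, 0.942 at 12 and 0.999 at 24. The period-adjusted model is an assumption of this check; the plan does not specify it.

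**The case against.** The best defence is that Section III selects while Section VI enrols. The Screening Visit text places enrolment after screening, and its examination and laboratory results can exclude people already called study subjects. The paragraph in Section III that requires ASA P1 also describes the history and examination used to rule out disease, so it may be speaking of people not yet cleared. On this reading only Section VI states an enrolment figure, it is derived and reproducible, exposure is 24 visits, and the defect is one missing clause. No estimate or error rate changes either way.

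Much of this stands. The screening reading is plausible, the 48 visits arise only if 24 are enrolled and all complete both visits, and the power of the sizing test is not in danger. But the document never says that 24 is a screening number, and a recruitment figure should not depend on the reader inferring a distinction between two verbs. The t-test and variance-label points are secondary, and the main point does not need them.

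**Conclusion.** The inconsistency is real. As written, the planned number of subjects is either 12 or 24, which means 24 or 48 anaesthesia visits. Only 12 is justified in the text. The larger number may serve another aim, but none is given a sample-size reason. This is not a finding of low power: on the stated z-test both 12 and 24 exceed 0.90, and 12 also does so under either t-test. Only the statement that 9 subjects suffice depends on treating the SD as known. The power figures rest on a difference of 3 and on 9 being the variance of the within-subject difference. The opening pages of the document were not in the text available for review, so a reconciling statement there cannot be excluded. Because sample size is a figure the trial relies on and the correction is nearly free, it should be made.

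**What to change.** Put one enrolment number in Sections III and VI, fix it before any look at the data, and state the power for that number.

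- If 24 is a screening number, say in Section III that up to 24 volunteers will be screened to enrol 12.
- If 24 are to be enrolled, change 12 to 24 in Section VI and give the reason.
- If 12 per visit order is meant, say so and justify the total of 24.

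Two minor edits can be made together with this: label 9 as the variance of the within-subject difference, and name the planned test of the Global Precedence score so that the claim about 9 subjects matches it.

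The cost is wording only if 12 is the number, or a short justification in Section VI if 24 is. No new data or procedures are needed.

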## II. SPECIFIC AIMS

The specific aims of this study are:

**AIM 1:** To use high-density EEG recordings to characterize the different brain-states induced by the anesthetic vapor, sevoflurane.

**Hypothesis 1a.** The onset and stable maintenance of sevoflurane-induced beta oscillations will signify a sedative brain state with a probability of response to auditory and nociceptive stimuli that approaches the awake state.

**Hypothesis 1b.** The onset and stable maintenance of highly coherent sevoflurane-induced frontal alpha and theta oscillations will signify a brain-state approaching a zero probability of response to auditory and nociceptive stimuli.

**Hypothesis 1c.** Sevoflurane-induced large slow oscillations (at maximum amplitude) and burst suppression will signify a brain state with a zero probability of response to auditory stimuli.

**Hypothesis 1d.** Return of consciousness will be preceded by return of gamma oscillations and the loss of large amplitude slow, theta, alpha and beta oscillations.

**AIM 2:** To use high-density EEG recordings to understand the neural-circuit mechanism of action of ether anesthetics.

**Hypothesis 2a.** The administration of an N-methyl-D-aspartate receptor antagonist (ketamine) during sevoflurane-induced unconsciousness (putative  $\gamma$ -aminobutyric acid mechanism) will antagonize and significantly diminish the amplitude of the alpha and slow oscillations.

**Hypothesis 2b.** The administration of an N-methyl-D-aspartate receptor antagonist (ketamine) during sevoflurane-induced unconsciousness (putative  $\gamma$ -aminobutyric acid mechanism) will produce globally non-coherent beta oscillations that are sufficient to maintain a brain state with a zero probability of response to auditory stimuli.

**Hypothesis 2c.** The administration of an N-methyl-D-aspartate receptor antagonist (ketamine) during sevoflurane-induced unconsciousness (putative  $\gamma$ -aminobutyric acid mechanism) will antagonize the effects of sevoflurane on airway collapsibility by mediated by  $\gamma$ -aminobutyric acid inhibition on the hypoglossal motor neuron.

**AIM 3:** To use inflammatory profiling of serum to understand the effect of sevoflurane on systemic inflammation

**Hypothesis 3a:** We hypothesize that sevoflurane-anesthesia will be associated with increased levels of pro-inflammatory cytokines interleukin 6 and TNF-alpha.

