The following questionnaires will be administered during the baseline and recovery periods to assess pain intensity and quality, measure levels of emotional distress and cognitive state.:

- PROMIS Numeric Rating Scale V1.0 – Pain Intensity 1A;
- PROMIS Scale v2.0 – Neuropathic Pain Quality 5a;
- PROMIS Scale v2.0 – Nociceptive Pain Quality 5a.
- PROMIS Item Bank v.1.0 – Emotional Distress-Anxiety Short Form 8A (modified to ask for symptoms experienced within the past hour);
- PROMIS Item Bank v.1.0 – Meaning and purpose Short Form 8A;
- PROMIS Item Bank v.1.0 – Positive Affect Short Form 15A (modified to ask for symptoms experienced within the past hour);
- The Clinician Administered Dissociative States Scale (CADSS)

In addition, inattention, memory and risk assessment cognitive domains will be evaluated using the following three computer presented neurocognitive tasks respectively: 1) Global Precedence, 2) Operation Span and 3) Columbia Card tasks (<https://www.neurobs.com>).

Recording of physiological measurements (blood pressure, heart rate, pulse oximetry, end tidal carbon dioxide, and galvanic skin response) will be initiated and maintained from the beginning of the study protocol until the subject is in the post-anesthesia recovery phase.

The total time under sevoflurane will be approximately the same for both protocols.

During the administration of sevoflurane the subject will be assigned to complete the following auditory task:

Auditory task: Subjects will be asked to respond to auditory stimuli via button-press jittered at random between 4 and 8 second intervals in order to resolve the precise period at which loss and recovery of consciousness/responsiveness occurred at a fine temporal scale. The auditory stimulus will consist of two components, a train of “clicks” and the command “click the mouse”. Subjects will be asked to respond by pressing the mouse in the hand. The sound intensity for all stimuli will not exceed 85 dB sound pressure level (SPL), in accordance with National Institute for Occupational Safety and Health guidelines for occupational noise exposure (U.S. Department of Health and Human Services and National Institute for Occupational Safety and Health, 1998).

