Behavioral Analysis: The probability of response to the click and verbal stimuli and the difference in probability of response will be estimated by using Bayesian Monte Carlo methods to fit a state-space model to these data. To perform group-level analyses, we will align the behavioral data across subjects with respect to each subject's LOC time for induction and with respect to each subject's ROC time for emergence. We will then pool the responses within bins. The pooled data will be used to estimate group-level probabilities of response using the state-space model.

Spectral Analysis: We will compute spectrograms for all subjects using the multitaper method. We will also compute group-level baseline-normalized spectrograms for induction and emergence by taking the median across subjects with the data aligned to the LOC and ROC time points, respectively. To determine if the group-level spectrogram is significantly greater than baseline, we will perform a two-group-test as implemented in chronux.

Eigenvalue and Modal Projection Analyses: We will perform an eigenvector decomposition analysis of the cross-spectral matrix to identify the principal modes of oscillation in the conscious and unconscious states and to analyze how activity within these principal modes change through time. We will estimate the cross-spectral matrices  $P_{\text{baseline}}(f)$  and  $P_{\text{unconscious}}(f)$  at each frequency  $f$  using the multitaper method using data from the full baseline period, and segments of at least 5 min extending from LOC to ROC, respectively, for each subject. An eigenvalue decomposition of the median cross-spectral matrix at each frequency will be performed. Each eigenvector describes a

coherent spatial distribution or mode of oscillation, and the corresponding eigenvalue quantifies the power in this mode. We then use modal projection analysis to characterize how power within principal modes change as a function of time. A permutation-based procedure will be performed to assess statistical significance for the modal projection analysis.

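### Hypotheses 1a-1c predict response probability given an EEG state, but the planned analyses condition on loss and return of consciousness and never estimate response within an EEG-defined state

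*Combined protocol and SAP*

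**What the plan says.** **Hypotheses (II. Specific Aims).** Each starts from an EEG pattern and predicts behaviour.
- 1a: stable beta oscillations "will signify a sedative brain state with a probability of response to auditory and nociceptive stimuli that approaches the awake state".
- 1b: highly coherent frontal alpha and theta "will signify a brain-state approaching a zero probability of response to auditory and nociceptive stimuli".
- 1c: maximal slow oscillations and burst suppression "will signify a brain state with a zero probability of response to auditory stimuli".

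**Behavioural data (Study Visit 1 and 2, Auditory task).** Stimuli answered by button press are "jittered at random between 4 and 8 second intervals". The stated purpose is "in order to resolve the precise period at which loss and recovery of consciousness/responsiveness occurred at a fine temporal scale". No rule turns presses into an LOC or ROC time.

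**Behavioural analysis (VI. Biostatistical Analysis).** A state-space model is fitted to the responses. For the group level the plan says "To perform group-level analyses, we will align the behavioral data across subjects"; time zero is the subject's own LOC in induction and own ROC in emergence. Responses are pooled in bins, and "The pooled data will be used to estimate group-level probabilities of response using the state-space model".

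**EEG analysis (same section).** Group spectrograms are aligned to LOC and ROC and tested against baseline. The unconscious cross-spectral matrix uses stretches of five minutes or more between LOC and ROC. The phase-amplitude analysis does not use responses. The one stated link between behaviour and EEG is optional video of spontaneous movement, which is not response to a stimulus.

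**The concern.** The hypotheses and the analyses condition on opposite things. The hypotheses ask how often a subject responds when the EEG shows a given pattern. The analyses ask what the EEG looks like once the subject has stopped responding. A pattern may be present throughout unresponsiveness and also appear while the subject still responds. The second question would then return a clear result while 1b or 1c was false.

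Aim 1 is to characterise the brain states induced by sevoflurane, and 1a-1c carry its claims about what each state means for responsiveness. If the plan is followed exactly, the report would have spectra around LOC and ROC and a response curve around LOC and ROC, but no figure for response within any named state and no interval behind a claim of zero. The aligned curve might then be offered as support for 1b or 1c, although it is not conditioned on the EEG and may be partly shaped by how time zero was chosen.

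**Working it through.** **Step 1. What is needed against what is planned.** This step is a reading of the text; the plan gives no figure on this point to reproduce.

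| Needed for 1a-1c | In VI. Biostatistical Analysis |
|---|---|
| Criteria for the beta, alpha/theta and slow/burst-suppression states | None |
| States marked independently of responses | None; EEG segments are chosen by LOC and ROC |
| P(response given state), with an interval | None; response is estimated against time from LOC or ROC |
| A meaning for zero, approaching zero and approaching awake | None |

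**Step 2. Why the planned quantities do not stand in.** By Bayes' rule,

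P(response | state) = P(state | response) × P(response) / P(state).

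The LOC-to-ROC spectra describe the EEG during unresponsiveness. The right-hand side also needs how often the state occurs while the subject is responding, and how often it occurs overall. Neither is tabulated, because no state is defined.

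**Step 3. The nociceptive part.** Hypotheses 1a and 1b also name nociceptive stimuli. Study Visit 1 and 2 gives the cuff stimulus once before and once after the study period, so no nociceptive response is described within the anaesthetic states. Those passages must be reconciled. The rest of this point concerns auditory stimuli only.

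**Step 4. The caveat on the aligned curve.** Assumptions, none of them in the documents: LOC is the first of five consecutive misses; 140 stimuli per subject about 6 s apart (the midpoint of 4 and 8 s); independent responses; raw pooled means with no smoothing. The true probability follows a logistic decline of the given width in stimuli, or stays constant.

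| True response | 5 before LOC: observed / true | First 5 from LOC | Stimuli 6-10 |
|---|---|---|---|
| Logistic, width 2 | 68% / 54% | 0% / 15% | 2% / 2% |
| Logistic, width 10 | 55% / 38% | 0% / 28% | 20% / 20% |
| Logistic, width 20 | 55% / 40% | 0% / 35% | 30% / 30% |
| Constant 40%, no transition | 56% / 40% | 0% / 40% | 40% / 40% |

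The 0% restates the rule: five misses are required, so five misses are seen. Five stimuli at 6 s is 5 × 6 = 30 s, after which observed and true rates agree.

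Other assumed rules change the size. Using the point where a smoothed response estimate crosses 0.5, the gap in the first five stimuli was about 6 to 24 points, depending on the smoother and the width. Placing LOC just after the last response gave 0% against 7-9%.

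**Step 5. What a zero can support.** Five minutes at one stimulus per 6 s is 300 / 6 = 50 stimuli. With no responses among 50 independent stimuli, the one-sided 95% upper bound for that subject is 1 − 0.05^(1/50) = 5.8%. Serial dependence would raise it. If none of 12 subjects responds, the upper bound on the proportion of people who would respond at all is 1 − 0.05^(1/12) = 22%; with 24 subjects it is 1 − 0.05^(1/24) = 12%. Both enrolment numbers appear, 24 under Subject Selection and 12 under Biostatistical Analysis.

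**The case against.** **The ingredients are present.** The state-space model is introduced before any alignment, spectrograms are computed for every subject, modal power is followed through time, and stimulus triggers are recorded with the EEG. An analyst could join these. That stands, and it makes the repair cheap. The joining step is still not in the plan, and without state criteria fixed beforehand it would be done after seeing both series.

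**Event alignment is an ordinary descriptive summary.** This also stands. No test is attached to the aligned response curve, and alignment to ROC suits Hypothesis 1d, which concerns what precedes return of consciousness.

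**A reader might infer that LOC and ROC certainly come from the button presses.** The documents do not say so. The Auditory task paragraph makes presses the likeliest source, but it states a purpose and not a rule. Loss of consciousness also appears as a clinical event under Airway Management, and video of arousal is optional.

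**A reader might infer that the whole fall to zero is manufactured by the alignment.** The documents do not support that either. Under the five-miss rule the distortion ends with the rule's own window; with no true transition, the curve returns to 40%. LOC-to-ROC segments of five minutes are ten times the 30 s affected. A sustained zero well after LOC would be a real finding. Even if LOC were placed after the last response, a run of 50 misses has probability 0.95^50 = 7.7% when the true response rate is 5%, so long runs point to a rate that is truly low.

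**Conclusion.** The point holds on the text alone: 1a-1c have no planned estimate, interval or test of the quantity they predict. This rests on no simulation and no assumption about LOC.

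The circularity is a secondary caveat. It depends on LOC and ROC being read from the same presses (implied, not stated) and on an unstated rule. Under the five-miss rule it amounts to 0% observed against 15-35% true in the first five stimuli, for logistic widths of 2 to 20, and it is gone by stimuli 6-10. Smoothing by the state-space model would blunt the step, and per-subject fits on their own time axis are not affected by the alignment. The caveat is reason not to cite the curve near time zero as evidence for 1b or 1c. It is not reason to doubt a sustained loss of response.

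This should be changed before analysis. It does not call the data collection for the auditory part of Aim 1 into question.

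**What to change.** 1. **EEG states.** Fix criteria in advance for each state named in 1a-1c: frequency band, power or coherence threshold, and minimum duration, since 1a and 1b speak of stable maintenance. Mark the states in each subject from the EEG alone, by someone or some algorithm blind to the button presses.
2. **Estimand and model.** Estimate the probability of response to the auditory stimuli within each state, with subject as the unit. A hierarchical logistic model, or a state-space model with EEG state as a covariate, would serve.
3. **Bounds.** Report zero and approaching zero as an upper interval limit judged against a value set beforehand. For 1a, name the awake reference period and the margin that counts as approaching it.
4. **LOC and ROC.** State the rule and the data it uses. Keep the LOC/ROC-aligned response curve as descriptive, and do not offer it as evidence for 1b or 1c.
5. **Nociception.** Reconcile 1a and 1b with the stated cuff timing.

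The cost is plan wording and a modest extra analysis of auditory and EEG data already being collected. The real effort is agreeing the EEG-state criteria before anyone looks at the responses.
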